2.2.2. Clinical Drug Metabolism and Pharmacokinetics

Coadministration with a high-fat meal increased C_{max} by 22% and AUC_{0- ∞} by 30% following a single dose of itacitinib 200 mg compared with administration in the fasted state. This increase is not clinically significant, and itacitinib may be administered without regard to food. Itacitinib displays supraproportional PK, that is, exposure increases greater than proportionally with increasing dose.

A single dose of three 100 mg SR3 tablets of itacitinib followed by an oral solution of [¹⁴C]itacitinib adipate approximately 500 μ Ci free base equivalent was administered to 7 healthy participants in Study INCB 39110-109. A mean of 71.7% of the dose was recovered in feces, and 24.5% was recovered in urine through the last collection interval. The overall mean recovery of radioactivity in urine and fecal samples was 96.2% by the end of the 240-hour study period. No major metabolites (\geq 10% of total drug-related material) were detected in plasma, and itacitinib was the major circulating species in plasma. Itacitinib was the major species in urine and feces. All metabolites identified in urine and feces accounted for < 10% of the excreted dose each.

Based on data from the renal impairment Study INCB 39110-122, total (AUC_{0- ∞}) and maximal exposure (C_{max}) increased by 2.23-fold (90% CI: 1.56, 3.18) and 1.65-fold (90% CI: 1.13, 2.39), respectively, in participants with severe renal impairment compared with participants with normal renal function. However, there was no notable change in total or maximal exposure in participants with end-stage renal disease receiving dialysis predose or 4 hours postdose.

In participants with moderate hepatic impairment, total (AUC_{0- ∞}) and maximal exposure (C_{max}) increased by 2.51-fold (90% CI: 1.54, 4.08) and 1.95-fold (90% CI: 1.14, 3.35), respectively, compared with normal participants (Study INCB 39110-113). In participants with severe hepatic

impairment, total ($AUC_{0-\infty}$) and maximal exposure (C_{max}) increased by 4.08-fold (90% CI: 2.41, 6.89) and 3.48-fold (90% CI: 1.94, 6.23), respectively, compared with normal participants.

Study INCB 39110-115 demonstrated that, while itacitinib may increase serum creatinine in some participants, there was no effect on GFR as measured by iohexol clearance.

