A post-hoc ECG exposure-response analysis was conducted to assess the cardiac safety of itacitinib using data from the first-in-human study, INCB 39110-101. Itacitinib at the studied doses did not have a relevant effect on cardiac conduction. A QTc effect exceeding the threshold of concern (10 ms) can be excluded within the observed range of itacitinib plasma concentrations (ie, up to \sim 13,000 nM, which is expected to be well-above the maximum concentration expected in various subpopulations [eg, renal impairment] receiving therapeutic itacitinib).

In a pilot study in acute GVHD participants (Study INCB 39110-108), characterization of the PK of itacitinib after single and multiple doses of itacitinib was performed. In this study, doses of 200 mg or 300 mg QD were administered and appear to display similar PK in this participant population, noting the small sample size (see [Table 4](#)). Additionally, participants who were concomitantly on a strong CYP3A4 inhibitor, mainly posaconazole, appeared to have exposures ($AUC_{0-\tau}$) approximately 2 \times higher than those who were not concomitantly on a strong CYP3A inhibitor (see [Table 5](#)). Based on preliminary data, exposures following 200 mg QD were similar in a Phase 3 study in acute GVHD participants as compared to the pilot study. Additionally, based on preliminary data from this Phase 3 study, exposures in participants concomitantly receiving posaconazole were similar to those concomitantly receiving voriconazole, supporting similar dosing recommendations for itacitinib when coadministered with any strong CYP3A inhibitor regardless of the specific inhibitor.

Table 4: Summary of Itacitinib Steady-State (Day 7) Pharmacokinetic Parameters by Actual Dose Regimen

Actual Regimen	No. of Participants	C_{max} (nM)	t_{max} (h)	C_{tau} (nM)	AUC_{tau} (nM•h) ^a
200 mg QD	11	624 ± 340 (534)	4.0 (1.3, 7.0)	64.0 ± 79.3 (NC)	5560 ± 3430 (4700)
300 mg QD	13	781 ± 668 (484)	2.0 (0.0, 5.6)	53.1 ± 64.0 (NC)	5880 ± 5170 (4110)

NC = not calculable.

Note: Values are mean \pm SD (geometric mean), except t_{max} , which is median (min, max).

^a AUC_{tau} is calculated from time 0-24 hours postdose, where the 24-hour concentration is imputed from predose trough.

Table 5: Summary of Itacitinib Steady-State (Day 7) Pharmacokinetic Parameters by Actual Dose Regimens and Concomitant CYP3A4 Inhibitors

Actual Regimen	CYP3A4 Inhibitor ^a	No. of Participants	C _{max} (nM)	T _{max} (h)	C _{tau} (nM)	AUC _{tau} (nM•h)

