5. STUDY POPULATION

Deviations from eligibility criteria are not allowed because they can potentially jeopardize the scientific integrity of the study, regulatory acceptability, and/or participant safety. Therefore, adherence to the criteria as specified in the Protocol is essential. Prospective approval of Protocol deviations to recruitment and enrollment criteria, also known as Protocol waivers or exemptions, are not permitted.

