11. Participants who are currently breastfeeding.

12. Receipt of a prior investigational study agent within 4 weeks before screening visit.

Note: Participants who have received anti-CD19 IEC therapy on a study where cell infusion occurred greater than 4 weeks before the screening visit are NOT excluded.

13. Any condition that would, in the investigator's judgment, interfere with full participation in the study, including administration of itacitinib and attending required study visits (if outpatient); pose a significant risk to the participant; or interfere with interpretation of study data.

14. Inability of the participant to swallow and retain oral medication.

15. Participants with laboratory values at screening defined in [Table 8](#).

Table 8: Exclusionary Laboratory Values

Laboratory Parameter		Exclusion Criterion
Hematology		
a	Platelets	$\leq 10 \times 10^9/L$
b	Hemoglobin	$\leq 8 \text{ g/dL}$
Hepatic		
e	ALT	$\geq 2.5 \times \text{ULN}$ for age, $> 5 \times \text{ULN}$ in the presence of liver metastases
f	AST	$\geq 2.5 \times \text{ULN}$ for age, $> 5 \times \text{ULN}$ in the presence of liver metastases
g	Total bilirubin	$> 1.5 \times \text{ULN}$ or $> 3 \times \text{ULN}$ in the presence of documented Gilbert's syndrome (unconjugated hyperbilirubinemia)
Renal		
h	Creatinine clearance	
Participants ≥ 18 years of age: $\leq 50 \text{ mL/minute}$ based on Cockcroft-Gault formula.
 
Participants < 18 years of age: GFR < 15 based on revised Schwartz formula 2009.
 
The cutoffs for mild, moderate, and severe renal insufficiency based on Cockcroft-Gault are 60-90 mL/min, 30-59 mL/min, and 0-29 mL/min, respectively.
 
Note: Creatinine clearance necessitates a 24-hour urine sample before the blood draw to calculate. An estimated value is acceptable.

Cardiopulmonary		
i	Cardiac LVEF	$\leq 40\%$ confirmed by ECHO/multigated analysis
j	Adequate pulmonary function	$\geq \text{Grade 2 dyspnea}$ and $\geq \text{Grade 2 hypoxia}$

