6.4.2. Restricted Medications and Procedures

The following medications have restrictions on use during the treatment period of the study:

- Aspirin in doses exceeding 125 mg per day is not permitted. Low-dose aspirin (≤ 125 mg per day) is permitted unless clinically contraindicated.
- Coadministration with strong CYP3A inhibitors.
 - If the participant's medical condition requires treatment with posaconazole, itraconazole, voriconazole, mibefradil, or clarithromycin, a dose reduction of itacitinib is recommended (see below), as strong CYP3A inhibitors have been shown to increase exposure to itacitinib (see [Appendix B](#)).

Part 1 dose reduction: Itacitinib 200 mg QD may be reduced to 100 mg QD.

Part 2 dose reduction: Itacitinib 200 mg BID (or Placebo) may be reduced to 100 mg BID or placebo.

- The sponsor medical monitor may be consulted for advice when CYP3A inhibitors are considered.
- If concomitant administration of an anticoagulant/antiplatelet medication is indicated, then caution and enhanced monitoring is required. History of thrombocytopenia should be a factor in the choice of anticoagulant and dose.
- Tocilizumab and/or corticosteroids for CRS Grade 1 is not allowed. However, tocilizumab may be given as rescue medication for CRS Grade 1 if no improvement is observed within 72 hours from onset, and the participant's medical condition requires intervention per investigator judgment.

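### Protocol Table 8, row h: the renal cut-off for under-18s (GFR < 15) is looser than the adult limit and lets GFR 15-29 through at the full Part 1 dose (minor, Part 1 only)

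*Protocol*

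**What the plan says.** Protocol Section 5.2, Table 8, row h, sets the renal exclusion by age. Adults are out at 50 mL/min or less by Cockcroft-Gault. For participants under 18 the exclusion is "GFR < 15 based on revised Schwartz formula 2009", with no unit. The same cell adds: "The cutoffs for mild, moderate, and severe renal insufficiency based on Cockcroft-Gault are 60-90 mL/min, 30-59 mL/min, and 0-29 mL/min, respectively".

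Section 5.1 admits participants from age 12 in Part 1 and from age 18 in Part 2. Part 1 gives 200 mg QD. Section 6.1.3 allows a step down to 100 mg QD on the investigator's judgment, taking account of an adverse event or the participant's underlying condition. It contains no renal rule.

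On exposure, Section 2.2.2 reports an AUC ratio of 2.23 (90% CI 1.56 to 3.18) and, for Cmax, "1.65-fold (90% CI: 1.13, 2.39), respectively, in participants with severe renal impairment compared with participants with normal renal function". It goes on to say that "there was no notable change in total or maximal exposure in participants with end-stage renal disease receiving dialysis predose or 4 hours postdose". For strong CYP3A inhibitors, which the same section associates with roughly doubled exposure, Section 6.4.2 says "a dose reduction of itacitinib is recommended (see below), as strong CYP3A inhibitors have been shown to increase exposure to itacitinib"; the Part 1 step is again from 200 to 100 mg QD.

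**The concern.** The row is stricter for adults than for minors, and nothing visible explains why. The values it lets through for minors include 15-29. The cell itself labels that range severe on the Cockcroft-Gault scale, and severe is the non-dialysis renal category for which the protocol reports higher exposure. An adult with the same number is kept out.

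The protocol also treats two similar exposure rises differently. The drug interaction is named and a reduction is recommended. For the renal rise, both entry and dose rest on general judgment. What is at stake is dosing safety for a small number of adolescents in Part 1, not the validity of an efficacy analysis.

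**Working it through.** No planned sample size, power or alpha figure is involved, so there is no figure of the plan's to reproduce. The check compares the limits and then sizes the exposure.

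1. **Limits side by side** (Table 8, row h; Section 5.1).
   - Adults: excluded at 50 or below.
   - Under-18s: excluded below 15.
   - Values passing for under-18s and failing for adults: 15 to 50.
   - Part of that gap inside the cell's severe band (0-29): 15 to 29.
   - Part 1 is open from age 12, so the gap can arise there. Part 2 starts at 18, so it cannot.
   - The comparison is numeric only, because the two limits use different formulas and the under-18 limit has no unit.

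2. **Renal rise against the CYP3A rise** (Section 2.2.2 and Table 5, geometric mean AUC, potent inhibitor over none or mild).
   - Severe renal impairment: 2.23 (90% CI 1.56 to 3.18).
   - Inhibitor at 200 mg QD: 6250 / 3720 = 1.68 (n = 5 and 6).
   - Inhibitor at 300 mg QD: 6720 / 2320 = 2.90 (n = 7 and 6).
   - The renal ratio lies between the two inhibitor ratios, so calling the rises similar is fair, given very small groups.

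3. **Peak free concentration against the 500 nM level in Section 2.3.4.**
   - Free fraction implied by the Figure 3 note: 49 / 141 = 0.348.
   - Cmax at 200 mg QD with no or mild inhibitor (Table 5 geometric mean, n = 6): 492 nM.
   - Free Cmax: 492 × 0.348 = 171 nM.
   - In severe impairment: 171 × 1.65 = 282 nM.
   - Over the 90% CI: 171 × 1.13 = 193 nM to 171 × 2.39 = 409 nM.
   - This is a typical value from six participants with acute GVHD, not a bound for an individual. The protocol's worry at 500 nM is sustained exposure rather than a peak.

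4. **AUC against the Part 2 dose.** Assume that 24-hour AUC at 200 mg BID is twice that at 200 mg QD.
   - Severe impairment on 200 mg QD relative to 400 mg/day: 2.23 / 2 = 1.12.
   - Over the 90% CI: 1.56 / 2 = 0.78 to 3.18 / 2 = 1.59.

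5. **Number affected.** Neither document states how many under-18s were planned or enrolled, so no count can be derived.

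Steps 3 and 4 both assume that the renal ratios carry over to adolescents with a Schwartz GFR of 15-29. The documents do not say that the renal study included adolescents.

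**The case against.** The strongest reply is that this is a drafting query without a demonstrated consequence. Much of it stands.

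- **No harm is shown.** Typical free Cmax stays below 500 nM, and AUC is close to what Part 2 plans for adults. Section 9.10 counts as overdose only more than 400 mg in 24 hours. Section 2.2.2 excludes a QTc effect of concern up to about 13,000 nM, expected to be well above the "maximum concentration expected in various subpopulations [eg, renal impairment] receiving therapeutic itacitinib". A reader might infer that the row exposes adolescents to toxic concentrations; the documents do not support that.
- **Row h is not the only safeguard.** Exclusion 7 covers unresolved toxicity of Grade 2 or more from earlier anticancer therapy. Exclusion 13 covers any condition the investigator judges a significant risk. Section 6.1.3 allows the same dose step as Section 6.4.2, and neither is mandatory. Serum chemistry, which includes creatinine, is scheduled at most treatment visits. These may well protect such a participant, but none sets a renal number.
- **The severe label is borrowed.** The band is on the Cockcroft-Gault scale and the under-18 criterion uses Schwartz. The dialysis result also points the other way, although it does not describe an undialyzed participant at 15-29.
- **A reason may exist out of view.** The Investigator's Brochure is not available here and some protocol text is redacted, so only the absence of a visible reason can be claimed.
- **A limit of 30 leaves 30-50 open.** True. The documents give no exposure figure for moderate impairment, so they do not support going further.

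Two other inferences should be resisted. Section 5 says "Prospective approval of Protocol deviations to recruitment and enrollment criteria, also known as Protocol waivers or exemptions, are not permitted". A reader might take this to mean that anyone passing row h must be admitted. It bars letting ineligible people in; it does not compel entry, and exclusion 13 is itself a binding criterion. SAP Section 3.1 mentions 10 participants with ALL among about 62 in Part 1. A reader might treat that as a ceiling on under-18s, but it counts a disease, not an age group.

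**Conclusion.** The point holds as a minor design weakness confined to Part 1. The stated renal rule is looser for minors than for adults, lacks a unit and a visible reason, and lets through GFR 15-29, which probably corresponds to the non-dialysis band with a reported 2.23-fold AUC (90% CI 1.56 to 3.18). That conclusion rests on carrying both the Cockcroft-Gault band and the exposure ratio over to adolescents, which is an inference. The number of under-18s is unknown, and few or none are likely to have a GFR in that range. The Part 2 comparison, its power and its alpha are unaffected. It is worth changing because the change is cheap. Confidence is medium.

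**What to change.** In Table 8, row h, replace the under-18 criterion with: *GFR < 30 mL/min/1.73 m2 (revised Schwartz 2009)*. The value 30 follows from the cell's own severe band of 0-29. The unit is our proposal, since the row gives none, and the sponsor should confirm it.

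The cost is one table cell at the next amendment and, at most, a few adolescents excluded. The documents do not say whether Part 1 enrollment has closed. If it has, leave the cell alone and list in the study report any under-18 participant enrolled with GFR < 30, with the dose received.

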5.3. Lifestyle Considerations

Participants should be instructed to refrain from the consumption of pomegranates or pomegranate juice and grapefruit and grapefruit juice, as these are known to inhibit CYP3A enzymes and may increase the exposure to itacitinib.

5.4. Screen Failures

Screen failures are defined as participants who consent to participate in the clinical study but are not subsequently entered in the study within the 14-day screening period. At a minimum, the following information must be collected and entered into the eCRF: demography, screen failure details, and eligibility criteria.

Individuals who do not meet the criteria for participation in this study (screen failure) may be rescreened 1 time if the investigator believes that there has been a change in eligibility status.

Participants who rescreen must be assigned a new participant number, must be re-consented to participate in the study, and must repeat all screening procedures (laboratory assessments do not need to be repeated if done within 3 days of rescreening).

Tests with results that fail eligibility requirements may be repeated once during screening if the investigator believes the result to be in error.

5.5. Replacement of Participants

Participants who do not meet the eligibility requirements of the study may be replaced.

6. STUDY TREATMENT

6.1. Study Treatment Administered

[Table 9](#) presents the study treatment information.

Table 9: Study Treatment Information

	Study Treatment
Study treatment name:	Part 1: Itacitinib (all participants) Part 2: Itacitinib or placebo
Dosage formulation:	Sustained release
Unit dose strength(s)/dosage level(s):	100 mg tablets Part 1: 200 mg QD Part 2: 200 mg BID or placebo
Route of administration:	Oral
Administration instructions:	Study treatment should be taken with water and regardless of food. [REDACTED] [REDACTED]
Packaging and labeling:	Study treatment will be provided to sites in high-density polyethylene bottles as applicable by Incyte. No preparation is required. Each bottle will be labeled as per country requirement.
Storage:	Study treatment should be stored at ambient conditions (15°C-30°C or 59°F-86°F) as per the IB.

6.1.1. Study Treatment Preparation, Handling, and Accountability

The investigator or designee must confirm appropriate temperature conditions have been maintained during transit for all study treatments received and any discrepancies are reported and resolved before use of the study treatment.

Only participants enrolled in the study may receive study treatment, and only authorized site staff may supply or administer study treatment. All study treatment must be stored in a secure, environmentally controlled, and monitored (manual or automated) area in accordance with the labeled storage conditions with access limited to the investigator and authorized site staff.

The investigator (or designee) is responsible for study treatment accountability, reconciliation, and record maintenance (ie, receipt, reconciliation, and final disposition records). Inventory and accountability records must be maintained and readily available for inspection by the study monitor and are open to inspection at any time by any applicable regulatory authorities. The investigator or designee must maintain records that document:

- Delivery of study treatment to the study site.
- Inventory of study treatment at the site.
- Participant use of the study treatment including pill counts from each supply dispensed.
- Return of study treatment to the investigator or designee by participants.

The investigational product must be used only in accordance with the Protocol. The investigator will also maintain records adequately documenting that the participants were provided the specified itacitinib. These records should include dates, quantities, and any available batch or serial numbers or unique code numbers assigned to the investigational product and study participants.

Completed accountability records will be archived by the site. The investigator or designee will be expected to collect and retain all used, unused, and partially used containers of itacitinib until verified by the study monitor (unless otherwise agreed to by the sponsor). At the conclusion of the study, the investigator or designee will oversee shipment of any remaining itacitinib back to the sponsor or its designee for destruction according to institutional SOPs. If local procedures mandate on-site destruction of investigational supply, the site should (where local procedures allow) maintain the investigational supply until the study monitor inspects the accountability records in order to evaluate compliance and accuracy of accountability by the investigative site. At sites where the itacitinib is destroyed before monitor inspection, the monitors rely on documentation of destruction per the site SOP.

Further guidance and information for the final disposition of unused study treatments are provided in the Pharmacy Manual.

See [Appendix C](#) for instructions for participants for handling itacitinib.

6.1.2. Study Treatment Compliance

Compliance with study treatment should be emphasized to the participant by the site personnel, and appropriate steps should be taken to optimize compliance during the study. Compliance with study treatment will be calculated by the sponsor based on the drug accountability or dose

administration record documented by the site staff and monitored by the sponsor/designee. Participants will be instructed to bring all tablets with them to the study visits in order for site personnel to conduct tablet counts to assess itacitinib accountability. The drug accountability documentation or dose administration record will be used by the sponsor to calculate treatment compliance.

6.1.3. Dose Modifications for Itacitinib

Part 1

This Protocol includes a treatment regimen which is defined as follows: itacitinib beginning on Day -3 of itacitinib 200 mg QD through Day 26.

If a dose reduction of itacitinib from 200 mg QD to 100 mg QD, outside of the treatment regimen, is warranted in the judgment of the principal investigator, and in consultation with the medical monitor (whenever possible), while taking into account either the relatedness of an AE to the study treatment and/or the participant's underlying condition, then the dose reduction may be allowed. There will be no further dose reductions below 100 mg QD.

If a dose interruption is needed, the sponsor/medical monitor should be contacted.

Safety concerns should be discussed with the sponsor immediately upon occurrence or awareness to determine whether the participant should continue or discontinue study treatment.

Part 2

The treatment regimen in Part 2 is defined as 200 mg BID or placebo.

If a dose reduction is required, from 200 mg BID to 100 mg BID, the participant may take 1 tablet of study treatment instead of 2 tablets.

6.1.4. Criteria for Permanent Discontinuation of Study Treatment

The occurrence of unacceptable toxicity not caused by the underlying disease will require that study treatment be permanently discontinued. See Section [7.1.2](#) for discontinuation procedures.

Unacceptable toxicity is defined as follows:

- Occurrence of an AE that is related to study treatment that, in the judgment of the investigator or the sponsor's medical monitor, compromises the participant's ability to continue study-specific procedures or is considered to not be in the participant's best interest.

